4.3.1.3 SAEs

4.3.1.3.1 Last Vaccination

Last vaccination before an SAE will use the same methodology as the last vaccination before an unsolicited non-serious AE as described in Section 4.3.1.2.4.

4.3.1.3.2 Time of onset

[figure not shown]
Time of onset will be computed using the same methodology than for unsolicited non-serious AEs as described in Section 4.3.1.2.5.

4.3.1.3.3 Duration

Duration will be computed using the same methodology than for unsolicited non-serious AEs as described in Section 4.3.1.2.5.

4.3.2 Immunogenicity

4.3.2.1 Computed Values for Analysis

4.3.3 Efficacy

Not applicable.

4.3.4 Derived Other Variables

4.3.4.1 Duration of a Subject in the Trial

The duration of a subject in the study is computed as follows: maximum (date of visit, date of termination form) – V01 date +1.

4.3.4.2 Duration of the Trial

The duration of the study is computed as follows: maximum of all subjects (date of visit, date of termination form) – minimum for all subjects (date of V01) +1.

4.3.4.3 Age calculation

The age of a subject in the study is computed as follows:

Age in years: $(\text{Date of 1st injection} - \text{Date of birth} + 1) / 365.25$

Following age groups will be derived:

18 to 40 years: from 18th birthday date to the last day before the 41st birthday date

41 to <65 years: from 41st birthday date to the last day before the 65th birthday date

5 Statistical Methods and Determination of Sample Size

The statistical analyses will be performed under the responsibility of the Sponsor's Biostatistics platform using SAS® Version 9.4 software or later.

The statistical analysis will be performed in 2 steps: first, all the data collected on the period D0-D56 will be analyzed, and then the data up to M7 will be added to the first statistical report.

The results of the statistical analysis will be available in the final clinical study report (CSR).

For descriptive purposes, the following statistics will be presented:

Table 5.1: Descriptive Statistics Produced

| | | |
|---|-------------------------------------|---|
| Baseline characteristics and follow-up description | Categorical data | Number of subjects. Percentage of subjects. |
| | Continuous data | Mean, standard deviation, quartiles, minimum, and maximum. |
| Clinical safety results | Categorical data | Solicited: Number and percentage (95% CIs) of subjects. Unsolicited: Number and percentage (95% CIs) of subjects, and number of events. |
| Immunogenicity results | Categorical data (cutoff) | Number and percentage (95% CIs) of subjects. |
| | Continuous data (titer/data) | Log10: Mean and standard deviation. Anti-Log10 (work on Log10 distribution, and anti-Log10 applied): Geometric mean, 95% CI of the geometric mean, quartiles, minimum, and maximum. Graphical representation by Reverse Cumulative Distribution Curve (RCDC). |

The confidence interval (CI) for the single proportion will be calculated using the exact binomial method (Clopper-Pearson method), quoted by Newcombe (1), i.e., using the inverse of the beta integral with SAS®.

For immunogenicity results, assuming that Log₁₀ transformation of the titers/data follows a normal distribution, at first, the mean and the 95% CI will be calculated on Log₁₀ (titers/data) using the usual calculation for normal distribution (using Student's t distribution with n-1 degree of freedom), then antilog transformations will be applied to the results of calculations, in order to provide geometric means (GMs) and their 95% CI.

GM is defined as follows:

$$GM = \left(\prod_{i=1}^n y_i \right)^{1/n} = 10^{\left(\frac{1}{n} \sum_{i=1}^n \log_{10}(y_i) \right)}$$

where (y_1, y_2, \dots, y_n) are the observed titers or individual ratios for each subject.

5.1 Statistical Methods

5.1.1 Hypotheses and Statistical Methods for Immunogenicity Objective

5.1.1.1 Hypotheses

No hypothesis will be tested for the immunogenicity objective.

5.1.1.2 Statistical Methods

5.1.1.2.1 Immunogenicity

The descriptive immunogenicity analysis at D0, D14, D28, D42 and M7 will be performed to document immunogenicity of the 5 groups.

5.1.1.2.1.1 Descriptive Immunogenicity

For all the subjects, a descriptive analysis for pre dose 1 (D0), pre dose 4 (D14), pre dose 5 (D28), 14 days post dose 5 (D42) and 6 months after the last injection (M7) will present the following statistics for the rabies virus neutralizing antibody (RVNA) titers in each randomized vaccine group:

- Number of subjects with RVNA titer available
- Number and percentage of subjects with RVNA titer ≥ 0.2 (LLOQ) IU/mL and 95% CI of the proportion
- Number and percentage of subjects with RVNA titer ≥ 0.5 IU/mL, and 95% CI of the proportion
- Number and percentage of subjects with complete neutralization at the starting dilution (1/5) of the RFFIT assay
- GMTs and 95% CI of RVNA titers
- GM of individual titer ratio (GMTR):
 - D14/D0
 - D28/D0
 - D42/D0

- M7/D0
- Distribution of titers (minimum, Q1, median, Q3, maximum)
- Log₁₀: mean and its standard deviation (SD)
- Ratio of GMT at D14, D28 and D42 between:
 - Each VRVg group (VRVg-2 low, medium and high dosages and VRVg- 1 group) versus Imovax® Rabies
 - Each VRVg-2 group (VRVg-2 low, medium and high dosages) versus VRVg-1
 - VRVg-2 medium and high dosages versus low dosage
 - VRVg-2 high dosage versus medium dosage

The lower and upper limits of the two-sided 95% CIs of the proportions will be computed using the exact binomial method (Clopper-Pearson method) (1). For the ratio of GMTs between VRVg and Imovax® Rabies, the 95% CI will be obtained by antilog back-transformations of the CI of the difference [log₁₀(GMT VRVg)-log₁₀(GMT Imovax Rabies)] obtained using the usual calculation for normal distribution.

The complete descriptive immunogenicity data will be analyzed according to randomization group in FAS population. The main parameters, defined as GMTs and percentages of subjects with titers ≥ 0.5 IU/mL will also be described on the PP population.

Additionally, RCDC will be plotted in all vaccine groups, at D0, D14, D28, D42 and M7. Boxplots and density distribution of RVNA titers at D14, D28 and D42 will also be produced. All these figures will be plotted on the FAS population.

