1.4 Rationale for the Trial

The main objective of VRV11 is to define the VRVg-2 vaccine dosage [REDACTED], before embarking in large phase III non-inferiority studies including pre- and post-exposure regimens. This study involves the testing of a modified formulation of VRVg vaccine (VRVg-2) [REDACTED] [REDACTED]

Briefly, three dosages of a reformulated VRVg vaccine (VRVg-2) [REDACTED] will be tested in parallel to the initial VRVg formulation (named VRVg-1) and Imovax Rabies. The three VRVg-2 dosages chosen (low, medium and high), will provide higher Ag amounts per dose than that of VRVg-1 tested in previous trials (VRV01, VRV08, VRV02, VRV04, VRV06) (Section 5.1.2; Table 5.2). Imovax Rabies, has been chosen as control, since it is the Sanofi Pasteur commercial rabies vaccine in the US. The choice will be carried out through the descriptive analysis of the immune response (in particular, the proportion of subjects with RVNA titers ≥ 0.5 international units (IU)/mL), the titers distribution and the GMTs, and the safety profile that results from administrating the different dosages/formulations tested. The immunogenicity objectives are descriptive and therefore the study is not powered to detect statistically significant differences in antibody responses or to assess non-inferiority to the control.

2 Trial Objectives

Immunogenicity

To describe the immune response induced by VRVg-2 (low, medium and high dosage) versus VRVg-1 and Imovax Rabies, at D14 (7 days after the third injection), at D28 (14 days after the fourth injection), at D42 (14 days after the last injection), and at M7 (6 months after the last injection).

Safety

To describe the clinical safety profile of VRVg-2 (low, medium and high dosage) versus VRVg-1 and Imovax Rabies after each vaccine injection.

The endpoints for the objectives are presented in [Section 9.1.1](#) (Immunogenicity) and [Section 9.2.2](#) (Safety).

3 Investigators and Trial Organization

This trial will be conducted in 5 centers in the US. The Principal Investigators and any sub-investigators at the individual sites will be coordinated by one Coordinating Investigator. Details of the trial centers, the Investigators at each center, and the Coordinating Investigator(s) are provided in the "Involved Personnel List" document.

Monitoring and data management activities will be conducted by a Contract Research Organization (CRO), under the responsibility of the Sponsor.

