6.6 Randomization and Allocation Procedures

An IRT system will be used. The full detailed procedure for randomization will be described in the Operating Guidelines given to the Investigator and the staff in charge of these operations at each site.

At V01 (D0), the qualified staff member will call the IRT system to assign a subject number. The subject number will consist of eight digits, the first three digits corresponding to the number of the center followed by five digits corresponding to a chronological order of enrollment. The IRT system will define which product (dose number) will be administered for each vaccination.

Randomization, managed by IRT system, will be performed using the permuted block method with stratification on centers. This guarantees, at any time and in each center, the right number of subjects with respect to the randomization scheme that has been defined for the trial.

Subject numbers should not be reassigned for any reason. The R&D Quality Assurance Department at Sanofi Pasteur will hold the randomization codes of doses in a secured location.

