7.3 Sample Storage and Shipment

During storage, serum tubes are to be kept in a freezer whose temperature is set and maintained at -20°C or below. The temperature will be monitored and documented during the entire trial. If it rises above -10°C for any period of time, the Clinical Logistics Coordinator must be notified. See the Operating Guidelines for further details.

Shipments to the laboratories will be made only after appropriate monitoring, and following notification of the Clinical Logistics Coordinator. Sera will be shipped frozen, using dry ice to maintain them in a frozen state, in the packaging container provided by the carrier. Again, temperatures will be monitored. Shipments must be compliant with the International Air Transport Association (IATA) 602 regulations.

Samples will be shipped to Global Clinical Immunology (GCI) at Sanofi Pasteur. The address is provided in the Operating Guidelines. Testing will be performed by the GCI laboratory or its designee.

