11.3 Data Review

A blind review of the data is anticipated through the data review process led by Data Management before database lock.

12 Statistical Methods and Determination of Sample Size

The statistical analysis will be performed in two steps:

A first statistical analysis will be performed when results on all immunogenicity and safety data collected up to D56, i.e. up to 28 days after the primary vaccination series will be obtained and locked.

A final statistical analysis will be performed when immunogenicity and safety results from D56 to M7 will be obtained and locked.

The analysis will be performed under the responsibility of the Sponsor's Biostatistics platform with the SAS software, at least version 9.4 (SAS Institute, Cary, North Carolina, USA).

The dose for further clinical development will be based on the safety and immunogenicity profiles of the 3 VRVg-2 dosages evaluated in this study in particular the proportion of subjects with RVNA titers ≥ 0.5 international units (IU)/mL, the Geometric Mean Titers and the titer

distribution at all time-points. The study is descriptive and no statistical testing between the groups is planned.

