3.1 Trial Design

This will be a multicenter, observer-blind, controlled, randomized, Phase II study.

A total of 320 subjects aged 18 to <65 years will be included in the study.

Each subject will receive one of the 2 formulations of the Purified Vero Rabies Vaccine - Serum Free (VRVg) or the Rabies Humain Diploid Cell Vaccine Imovax Rabies. Vaccination will be according to the ESSEN post-exposure schedule (i.e., a total of 5 injections [1 injection per day] administered at D0, D3, D7, D14 and D28) and human rabies immunoglobulins (HRIG) will be administered at D0. Subjects will be assigned to the VRVg-2 groups (low, medium and high dosage), VRVg-1 group, or Imovax Rabies group with a 2:2:2:1:1 allocation ratio..

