5.1.3.1.2 Covariate Exploration of the Immunogenicity Results

The possible influence on the immune response at D14, D28 and D42 of the following characteristics will be studied:

- 1) Gender
- 2) Age "18 to 40 years" and "41 to <65 years"
- 3) Race (only if more than 5% of subjects in several race categories)

4) Center

A descriptive table simplified to the most relevant immunogenicity parameters will be provided for each sub-population, e.g. males and females. A homogeneity Fisher test will be performed to compare the proportion of subject with an RVNA titer ≥ 0.5 IU/mL of each subpopulation inside each vaccine group. The rationale for the proposed test is to provide evidence of whether or not, some differences can be observed between subpopulations on GMTs and on the proportion of subjects with an RVNA titer ≥ 0.5 IU/mL.

These covariate analyses will be performed on the FAS population.

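### Randomisation is stratified by centre, but the confidence interval for the VRVg/Imovax GMT ratio has no centre term and is somewhat too wide if centres differ

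*SAP*

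**What the plan says.** Protocol 6.6 sets the allocation method: "Randomization, managed by IRT system, will be performed using the permuted block method with stratification on centers". Protocol section 3 gives the number of strata: "This trial will be conducted in 5 centers in the US". SAP 3.1 gives the allocation: "VRVg-1 group, or Imovax Rabies group with a 2:2:2:1:1 allocation ratio", which for 320 subjects means 80, 80, 80, 40 and 40.

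SAP 5.1.1.2.1.1 plans GMT ratios at D14, D28 and D42. On their precision it says: "For the ratio of GMTs between VRVg and Imovax® Rabies, the 95% CI will be obtained by antilog back-transformations of the CI" of the difference between the two log10 GMTs, by the usual normal-theory calculation. No stratification factor or other covariate enters.

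Centre appears in the immunogenicity analysis only as one of four characteristics in the exploratory SAP 5.1.3.1.2: "A descriptive table simplified to the most relevant immunogenicity parameters will be provided for each sub-population, e.g. males and females". That section adds Fisher tests on the proportion reaching 0.5 IU/mL. It does not alter the GMT-ratio interval.

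The same list of ratios includes "Each VRVg-2 group (VRVg-2 low, medium and high dosages) versus VRVg-1" and the comparisons between VRVg-2 dosages, for which no interval method is written.

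**The concern.** An analysis should normally reflect the factor by which randomisation was stratified. Permuted blocks within centre give each vaccine group nearly the same mix of centres, so differences in titre level between centres almost cancel in the contrast of two groups. The SD within each group, taken over all centres, still includes that between-centre variation. The unadjusted calculation therefore overstates the standard error of the ratio.

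What is at stake is precision. The interval is labelled 95% but would cover more, and the stratified design has already secured precision that the analysis does not use. The comparator groups have only 40 subjects each, so these intervals are wide to begin with. Description is the trial's only inferential output, and it feeds the choice of VRVg-2 dosage.

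**Working it through.** **Inputs from the documents.** Five centres (Protocol section 3); permuted blocks stratified on centre (Protocol 6.6); groups of 80, 80, 80, 40 and 40 (SAP 3.1 and 5.5); interval method without centre (SAP 5.1.1.2.1.1).

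**Assumed, because the visible text gives no figure.** Log10-titre SD 0.45; centre share of the log10-titre variance *s* from 0 to 20%; additive centre effects; equal centre sizes; pooled variance in the unadjusted interval. Simulations that generated the blocks used size 8.

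**The plan's own figures.** The plan shows no width for a GMT ratio to reproduce. Its visible precision figures are the exact binomial intervals in SAP Table 5.5. All five reproduce to the first decimal, for example 8/80 gives 4.4 to 18.8.

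**Number of ratios.** Four VRVg groups v Imovax, three VRVg-2 v VRVg-1, two v low dosage, and one high v medium: 4 + 3 + 2 + 1 = 10 per time point. An interval method is written for the first 4 and not for the other 6.

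**Width.** Let N be the two groups' combined size and σ² the total log10 variance. Under stratified blocks:

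- the true variance of the difference is about (1 − s)σ²(1/n₁ + 1/n₂);
- the unadjusted estimate is centred on σ²[(1 − s) + sN/(N − 2)](1/n₁ + 1/n₂), with N − 2 degrees of freedom;
- the two-group model with centre is centred on (1 − s)σ²(1/n₁ + 1/n₂), with N − 6 degrees of freedom.

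The half-width ratio, unadjusted to adjusted, is

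t(N−2) × √[(1 − s) + sN/(N − 2)] ÷ {t(N−6) × √(1 − s)}.

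For 80 v 40, N = 120, t(118) = 1.9803 and t(114) = 1.9810. At s = 5% the ratio is 1.9803 × √(0.95 + 0.05 × 120/118) ÷ (1.9810 × √0.95) = 1.026.

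**Coverage.** By the normal approximation, the unadjusted interval covers 2Φ(1.96/√(1 − s)) − 1.

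**Scale.** The limits are the ratio multiplied or divided by 10^[t × 0.45 × √(1/n₁ + 1/n₂)], with a further factor √(1 − s) in the exponent when centre is in the model. For 80 v 40 the unadjusted factor is 10^(1.9803 × 0.45 × √(3/80)) = 1.49. For 40 v 40 (VRVg-1 v Imovax) it is 1.59.

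| s | Excess width, 80 v 40 | Unadjusted coverage | Adjusted factor, 80 v 40 | Adjusted factor, 40 v 40 |
|---|---|---|---|---|
| 0 | −0.04% | 95.0% | 1.49 | 1.59 |
| 1% | 0.5% | 95.1% | 1.485 | 1.58 |
| 2% | 1.0% | 95.2% | 1.48 | 1.58 |
| 5% | 2.6% | 95.6% | 1.47 | 1.57 |
| 10% | 5.5% | 96.1% | 1.46 | 1.55 |
| 20% | 12.0% | 97.2% | 1.43 | 1.51 |

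**Simulation.** With 20,000 runs per setting, 80 v 40, and shares of 5%, 10% and 20%, the excess widths were 2.6%, 5.5% and 11.9%. Unadjusted coverage was 95.7%, 96.3% and 97.1%, and adjusted coverage stayed at 94.8–95.2%. With unequal centres (120/80/60/40/20) and 5% of samples missing, the excess widths were 2.5%, 5.3% and 12.0%.

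**Is stratification the cause?** A reference run with unstratified allocation (4,000 runs per setting, shares 5–20%) gave unadjusted coverage of 94.8–95.4%. The over-coverage therefore comes from stratifying and then leaving the strata out of the analysis.

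**In subjects.** At a 10% share, the precision not used in an 80 v 40 comparison is worth about 120 × (1/0.90 − 1) = 13 further subjects.

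**The case against.** The strongest reply is that nothing turns on this interval. Protocol section 12 says: "The study is descriptive and no statistical testing between the groups is planned". Dosage selection is tied to safety, the proportion reaching 0.5 IU/mL, the GMTs and the titre distribution; the GMT ratio is not named. This stands, and it is why the point is minor.

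The size rests on an assumed centre share, which may well be low. Subjects are healthy adults in one country, and one laboratory is the default: "Testing will be performed by the GCI laboratory or its designee". At shares of 1% and 2% the average gain is 0.5% and 1.0%, and the adjusted interval is narrower in only 54% and 66% of simulated datasets. This also stands.

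Other intervals in the SAP over-cover too. Clopper-Pearson coverage, averaged over true proportions of 0.70 to 0.99, is 96.8% for n = 80 and 97.4% for n = 40. That is more than the excess here at shares of 5–10%. It puts the matter in proportion, but it does not supply a reason to leave out the stratification factor.

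Adjusted ratios need not equal the quotient of the tabulated GMTs. With 5% missing samples and equal centres, they differ by a factor of at most about 1.03, 1.035 and 1.05 in 95% of simulated datasets, at shares of 5%, 10% and 20%. Average movements of the interval limit are comparable: 1.488/1.473 = 1.01, 1.488/1.458 = 1.02 and 1.488/1.427 = 1.04. This is a real inconvenience, met by keeping the raw GMTs and the unadjusted ratios in the report.

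Finally, the six ratios without an interval method are a separate gap in wording. One sentence could close it without any centre model, and it does not support the argument about centre.

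**Conclusion.** The concern holds as a low-priority improvement. The randomisation is stratified by centre, and the stated interval for the VRVg/Imovax GMT ratio ignores centre. If centres differ, that interval is on average too wide and its coverage is above 95%. The error is conservative and the ratio is not biased; no test, margin or claim depends on it.

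For centre shares up to 10% the excess width is at most about 5.5%. It reaches about 12% only at a 20% share, and vanishes if centres do not differ. The direction follows from the design; the size depends on the assumed centre share. The SD of 0.45 affects only the multiplicative factors, not the percentage excess or the coverage. Confidence in the practical importance is moderate, because the documents give no between-centre variance.

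**What to change.** In SAP 5.1.1.2.1.1, state that all ten GMT ratios and their 95% intervals at D14, D28 and D42 come from a linear model of log10 titre on vaccine group and centre, back-transformed. This also supplies a method for the six ratios that have none. Keep the raw group GMTs as planned, and report the unadjusted ratios as a sensitivity analysis.

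The cost is a few lines of text and one model per time point. A single five-group model assumes a common residual variance; fitting each pair separately avoids this. The five-group model also narrows the 80 v 40 interval by about 0.6% through extra degrees of freedom (t(311)/t(118) = 0.994), which is not counted in the gains above. A footnote should say that adjusted ratios can differ slightly from the quotient of the tabulated GMTs.

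If the sponsor prefers to keep the unadjusted interval, the minimum is to say that it does not account for the stratification and may be slightly conservative, and to extend the stated method to the other six ratios.

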5.5 Determination of Sample Size and Power Calculation

An arbitrary number of 80 subjects per VRVg-2 group and 40 subjects in both VRVg-1 and Imovax Rabies has been proposed.

Table 5.4:

In terms of safety, according to the occurrence rate of the observed AEs, 80 subjects will allow for the following 95% CI (Table 5.5).

95% CI calculations corresponding to anticipated AEs rates in VRVg-2 groups of 80 subjects.

Table 5.5: 95% CI calculations corresponding to anticipated AEs rates in VRVg-2 groups of 80 subjects

| Observed numbers | Observed % | 95% CI |
|------------------|------------|--------------|
| 8/80 | 10.0 | (4.4; 18.8) |
| 12/80 | 15.0 | (8.0; 24.7) |
| 16/80 | 20.0 | (11.9; 30.4) |
| 20/80 | 25.0 | (16.0; 35.9) |
| 24/80 | 30.0 | (20.3; 41.3) |

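### The GMT ratios are estimated without age, sex or centre, and only four of the ten listed ratios have a stated CI method; one supportive adjusted model would cover all ten

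*SAP*

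**What the plan says.** SAP 5.1.1.2.1.1 lists ratios of GMTs at D14, D28 and D42 for ten contrasts:

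- each of the four VRVg groups versus Imovax Rabies (4);
- each VRVg-2 dosage versus VRVg-1 (3);
- medium and high versus low VRVg-2 (2);
- high versus medium VRVg-2 (1).

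The interval method that follows is limited in scope: "For the ratio of GMTs between VRVg and Imovax® Rabies", "the 95% CI will be obtained by antilog back-transformations of the CI of the difference" of log10 GMTs, "obtained using the usual calculation for normal distribution". The other six contrasts have no interval method.

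Covariates appear in SAP 5.1.3.1.2, under exploratory analyses: "The possible influence on the immune response at D14, D28 and D42 of the following characteristics will be studied". The list is gender, age group, race (conditionally) and centre. The planned output is a simplified descriptive table per subpopulation, plus a Fisher test comparing subpopulations inside each vaccine group on the proportion at or above 0.5 IU/mL. Neither document plans a covariate-adjusted between-group ratio.

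Randomisation is "performed using the permuted block method with stratification on centers" (Protocol 6.6), "with a 2:2:2:1:1 allocation ratio" (SAP 3.1). On size, SAP 5.5 says: "An arbitrary number of 80 subjects per VRVg-2 group and 40 subjects in both VRVg-1 and Imovax Rabies has been proposed". Demographic data are collected at V01 (Protocol 5.1.4), and SAP 4.3.4.3 already derives age at first injection.

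**The concern.** Stratifying on centre leaves age (18 to <65 years) and sex balanced only by chance, and two arms have 40 subjects. Seven of the ten ratios involve one of those arms. The SAP itself treats age and sex as possible influences on titre at the time points used for the ratios. Yet the subpopulation tables can only reveal an imbalance; they do not correct a ratio for it. Centre shaped the allocation and is also on the SAP's list, but it is absent from the interval.

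At stake are some precision and the accuracy of a ratio once a particular imbalance has been seen. If an imbalance appears after unblinding and no adjusted analysis is prespecified, any adjustment made then is a post hoc choice. Separately, six ratios, including every comparison between VRVg-2 dosages, could be reported without an interval or with one chosen later.

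**Working it through.** **Plan's own figures.** 320 split 2:2:2:1:1 is 320/8 = 40 per unit, so 80/80/80/40/40, as stated. The Clopper-Pearson limits in SAP Table 5.5 reproduce in all five rows to one decimal (for example 8/80: 4.4 to 18.8). The readable text gives no precision figure for a GMT ratio and no planning SD for log10 titre.

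**Assumptions (none is a document figure).** Log10 SD 0.3 to 0.6; 50% male; age SD 13 years (a uniform spread over 18 to 65 would give 47/√12 = 13.6); age slope 0.003 to 0.01 log10 per year; share of log10 variance explained (R²) 2% to 10%.

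**Step 1: width of the unadjusted interval.** Let k = √(1/n₁ + 1/n₂). The ratio is multiplied and divided by 10^(t × SD × k).

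| Contrast | k | t(0.975) | CI factor, SD 0.3 | CI factor, SD 0.6 |
|---|---|---|---|---|
| 80 vs 80 | 0.158 | 1.975 | 1.24 | 1.54 |
| 80 vs 40 | 0.194 | 1.980 | 1.30 | 1.70 |
| 40 vs 40 | 0.224 | 1.991 | 1.36 | 1.85 |

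**Step 2: size of a chance imbalance.** The SD of the difference in proportion male is 0.5k. The SD of the difference in mean age is 13k. The shift in the ratio for a 1-SD age imbalance is 10^(slope × 13k).

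| Contrast | Sex, 1 SD | Age, 1 SD | Shift, slope 0.003 | Shift, slope 0.01 |
|---|---|---|---|---|
| 80 vs 80 | 7.9 points | 2.06 years | 1.4% | 4.8% |
| 80 vs 40 | 9.7 points | 2.52 years | 1.8% | 6.0% |

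For sex, at the 95% limit of imbalance (1.96 × 0.5k) and an assumed 1.5-fold sex effect, the ratio shifts by a factor 1.5^(0.98k): 1.065 for 80 vs 80, 1.08 for 80 vs 40 and 1.09 for 40 vs 40. All these shifts are small beside the factors in step 1.

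**Step 3: gain in precision.** The half-width falls by 1 − √(1 − R²). Allowing for chance imbalance in age and sex within a five-arm model multiplies the variance by about 1 + 2/312.

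| R² | 1 − √(1 − R²) | Net, five-arm model |
|---|---|---|
| 2% | 1.0% | 0.7% |
| 5% | 2.5% | 2.2% |
| 10% | 5.1% | 4.8% |

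If the covariates explained nothing, the same formula gives a loss of 0.3%. Centre uses four more degrees of freedom (five centres) out of more than 300; because it is the stratum, its imbalance should be slight.

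A five-arm model also pools the variance over all arms and raises the degrees of freedom. For 80 vs 40, t falls from 1.980 to 1.968, about 0.6%. That part of any narrowing does not come from age, sex or centre.

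**Step 4: is the unadjusted interval valid?** This was simulated with two arms, binary sex and age group, residual SD 0.45 and 8,000 runs per setting. Overall coverage of the unadjusted interval was 94.8% to 95.4%. In the 3% to 7% of runs with a sex imbalance above 20 points:

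- at a 2-fold sex effect, unadjusted coverage was 89%, against about 95% adjusted;
- at a 1.5-fold effect, it was 93%, against 94% to 95% adjusted.

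The conditional figures rest on few runs. The 89% for 80 vs 40 comes from 0.0389 × 8,000 ≈ 311 runs, with standard error √(0.894 × 0.106/311) ≈ 1.7 points. The 2-fold result is clear; the 1.5-fold difference is within noise.

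**The case against.** The strongest reply is that nothing here is an error. The trial is descriptive, tests no hypothesis and is not powered for group differences. Randomisation makes the unadjusted interval valid, and its width already allows for chance imbalance. This stands: a reader might infer that the ratios are biased or the intervals wrong, and neither the documents nor the simulation support that.

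A reader might also infer that adjustment would alter the dosage decision. Protocol 1.4 and the opening of Protocol section 12 name the proportion at or above 0.5 IU/mL, the GMTs, the titre distribution and safety. Neither names GMT ratios, and the proposal leaves the group GMTs alone. Choosing among the VRVg-2 dosages compares 80 with 80, where the effect is smallest; the arms of 40 matter only for comparisons with VRVg-1 or Imovax Rabies.

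It is also fair that listing age and sex as possible influences does not establish them as prognostic, that every effect size above is assumed, and that the planned baseline summaries and subpopulation tables would make an imbalance visible.

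What survives is narrower. Visibility is not correction, six ratios lack an interval method, and a prespecified model settles both at almost no cost.

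**Conclusion.** The point holds as an optional improvement, not as a defect. The stated method for the four ratios versus Imovax Rabies is unadjusted and valid on average, and the other six ratios have no stated interval method. Age, sex and centre are available at baseline, yet none enters a between-group ratio.

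The benefit is modest: intervals about 2% to 5% narrower if the covariates explain 5% to 10% of log10 variance, and under 1% narrower at 2%. A 1-SD age imbalance moves a ratio by about 1% to 5% (80 vs 80) or 2% to 6% (80 vs 40). These figures depend on the assumed age SD, slope and R². No error rate or sample size changes. The missing interval method for six contrasts needs no assumption: it can be read directly from the SAP.

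**What to change.** In SAP 5.1.1.2.1.1:

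- State the unadjusted 95% CI method for all ten GMT ratios, not only the four versus Imovax Rabies.
- Add a supportive analysis at each of D14, D28 and D42: one linear model on log10 titre across the five groups, with vaccine group, continuous age at first injection, sex and centre. Report back-transformed adjusted ratios with 95% CIs for the ten contrasts beside the unadjusted ones.
- Note that the model pools variance across arms, so the two sets of intervals can differ for reasons other than the covariates.
- Treat titres below the LLOQ as in the GMT calculation.
- Keep group GMTs and reverse cumulative distribution curves unadjusted.

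Cost: one model statement per time point and added columns in an existing table. No new data, visits or subjects.
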